# 6 STATISTICAL CONSIDERATIONS

## 6.1 Primary Endpoint

In order to determine the effectiveness of the Opening Doors to Early Intervention Program on child developmental status, our primary outcome for this aim is the Bayley-III cognitive subscale measured at 12 months follow-up.

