## 6.2 Secondary Endpoints

Secondary outcomes include the Bayley-III language, motor, and socioemotional subscales and the binary outcomes of whether patients complete EI referrals and services at 12 months.

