## 6.3 Control of Bias and Confounding

Randomization and allocation concealment are the primary means of avoiding bias. Analytic strategies will also be used to control for residual confounding: (1) Stratification will control for imbalance not controlled by design. (2) Additional potential confounders will be evaluated for any residual association with treatment and included in model as needed. (3) Post randomization effects: The primary source of bias will arise after randomization from dropout and loss to follow-up. To address this problem and avoid missing data, we shall implement the following measures: (a) incentives to each family to complete the study, (b) collection of multiple contact numbers and tracking of changes, and (c) contact all randomized participants, even if they do not continue with their clinical contacts. Baseline data collection will include questions about factors that predict potential dropout, such as current living situations and regularity of contact with health care providers. (4) Our analytic model for treatment effect will include not only potential confounders but also predictors of dropout, to be able to relax assumptions about the missing data process. (5) To investigate the possibly informative dropout (for reasons related to the intervention), we will implement sensitivity analyses (6) For missing values in any of the outcome measurement tools, we will implement formal methods of multiple imputation. (7) We shall account for all dropouts and check all baseline information in real time for both invalid values and missing items and then prompt the child's caregiver for any corrections or clarifications. Then, if any covariates remain missing, we shall implement multiple imputation. (8) Attenuation bias from non-compliance might also occur if the child remains

in the study but fails to adhere to all aspects of the intervention. To address this potential problem, and to estimate the effect of treatment in the presence of full compliance, we will implement the methods outlined by Small and colleagues and by Nagelkerke. However, the “as randomized” approach will remain the primary method for assessing statistical significance of the intervention.

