ODEI Study Statistical Analyses Plan

Title: The Opening Doors to Early Intervention Study (ODEI)

NCT Number: NCT03625115

Document Date: July 3rd, 2024

ODEI Study Statistical Analyses Plan

Aim 1: To test the effectiveness of the Opening Doors to Early Intervention Program on EI service use and child developmental status among poor minority children residing in an urban community.

- a. *Hypothesis 1a:* A greater proportion of children who are randomized to the intervention will complete EI referrals than children in the control condition at 12 months.

Analysis: Chi square analysis on the difference in completion of MDE by study arm and logistic regression on the difference in MDE completion by arm, controlling for sex, age, and primary care site.

- b. *Hypothesis 1b:* Among children eligible for EI services, children randomized to the intervention will initiate EI services at a greater rate & receiving a longer duration of EI services than children in the control condition.

Analysis: Chi square test on the difference in EI service initiation by arm and logistic regression, controlled for sex, age, and primary care site. Survival analysis with a Kaplan-Meier curve of EI duration of services by arm.

- c. *Hypothesis 1c:* As a result, children who are randomized to the intervention will have more favorable developmental outcomes than children in the control condition at 12 months.

Analysis: Logistic regressions to determine the difference in cognitive and language BSID III scores by arm, controlling for sex, age, and primary care site.

Variable Definitions:

- Completion of EI Referrals: Completion of Multidisciplinary Evaluation (MDE)
- Initiating EI services: Date of first early intervention service
- Duration of EI services: The time between the EI service initiation and discharge from early intervention OR 12 months from randomization (if discharge date is unavailable)
- Developmental outcomes: Language and cognitive composite scores from BSID III assessment.

Aim 2: To assess whether parent engagement mediates the effects of the Opening Doors to Early Intervention Program.

- a. *Hypothesis 2a:* Parent engagement will mediate the association between program participation and completion of EI referrals and participation in EI services (duration).

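### The SAP does not carry over the protocol's outcome hierarchy: Aim 1 ranks no outcome, sets language level with the primary cognitive score, and omits two secondaries

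*SAP*

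**What the plan says.** **Protocol.** Section 6.1 states that "our primary outcome for this aim is the Bayley-III cognitive subscale measured at 12 months follow-up", and 6.4.2.1 repeats it. Section 6.2 begins "Secondary outcomes include the Bayley-III language, motor, and socioemotional subscales" and adds two binary outcomes at 12 months, completion of EI referrals and completion of EI services. Section 6.4.2.1 treats duration of EI service use as a secondary analysis. The success criterion (3 points) and the 96% power in 6.5 refer to the cognitive score only.

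**SAP.** Aim 1 lists Hypotheses 1a, 1b and 1c without ranking them. The word primary occurs only in the phrase for the care site.
- 1a (referral completion): "Chi square analysis on the difference in completion of MDE by study arm and logistic regression on the difference in MDE completion by arm", with adjustment for sex, age and site.
- 1b (initiation): "Chi square test on the difference in EI service initiation by arm and logistic regression, controlled for sex, age, and primary care site". For duration, only a survival analysis with a Kaplan-Meier curve is named, and no test.
- 1c (development): "Logistic regressions to determine the difference in cognitive and language BSID III scores by arm, controlling for sex, age, and primary care site". The variable definitions read "Developmental outcomes: Language and cognitive composite scores from BSID III assessment".

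**Error control.** Neither document gives an alpha level, sidedness or a multiplicity rule. The nearest text is in protocol 6.3, where the as-randomized "approach will remain the primary method for assessing statistical significance of the intervention".

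**The concern.** The SAP is the document an analyst would follow, and it neither restates nor refers to the protocol's hierarchy. Working from it alone, one could not tell that a difference on language without one on cognitive does not meet the primary objective. One would also produce no motor or socioemotional results, although the protocol promises both, and no analysis of service completion as a binary outcome. Promoting one secondary while leaving out others, without explanation, invites a charge of selective reporting. For 1a and 1b (initiation), an unadjusted and an adjusted result could disagree, and nothing says which is the finding.

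**Working it through.** **1. Side by side**

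| Outcome | Protocol 6.1, 6.2, 6.4.2.1 | SAP Aim 1 |
|---|---|---|
| Bayley cognitive, 12 months | Sole primary; linear mixed model with practice clustering | Unranked; logistic regression |
| Bayley language | Secondary | Unranked, paired with cognitive |
| Bayley motor, socioemotional | Secondary | No analysis |
| EI referral completion | Secondary; mixed model | Unranked; chi-square and adjusted logistic |
| EI service completion | Secondary; mixed model | No analysis |
| EI service initiation | Not listed in 6.2 | Unranked; chi-square and adjusted logistic |
| EI service duration | Secondary analysis | Unranked; Kaplan-Meier curve, no test |

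**2. The plan's own figure: 96% power for the cognitive score**

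Inputs from protocol 6.5: difference 3 points; 130 control and 170 intervention completers; enrolment 50% versus 80%; EI effect 10 points with SD 1. Two-sided 0.05 is assumed. Reading the stated model as a mixture, the outcome variance is 100·p(1−p) + 1.
- Control: 100 × 0.5 × 0.5 + 1 = 26. Intervention: 100 × 0.8 × 0.2 + 1 = 17.
- SE = √(26/130 + 17/170) = √0.30 = 0.548. Power = Φ(3/0.548 − 1.96) = 99.98%.
- 96% is obtained with a total SD of about 6.94: SE = 6.94 × √(1/130 + 1/170) = 0.809, and Φ(3/0.809 − 1.96) = 96.0%.

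The 96% came from a simulation, and the documents give neither total SD nor alpha. The figure is therefore unverifiable rather than shown wrong, and the point here does not depend on it. What matters is that it was computed for one outcome.

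**3. False-positive chance if either Bayley score counts as a win**

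Assumed: two-sided 0.05 per test, no true effect, bivariate normal test statistics. Chance = 1 − P(|Z₁| < 1.96 and |Z₂| < 1.96). The correlation is in neither document.

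| Assumed correlation | Chance of at least one false positive |
|---|---|
| 0 | 1 − 0.95² = 9.75% |
| 0.5 | 9.1% |
| 0.7 | 8.4% |
| 0.9 | 7.0% |

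**4. The four Aim 1 endpoints with a named test** (referral completion, initiation, cognitive, language)
- All independent: 1 − 0.95⁴ = 18.5%.
- Cognitive–language correlation 0.65, others 0: 1 − 0.9144 × 0.95² = 17.5%.
- Cognitive–language correlation 0.65, others 0.4 (simulation): about 16%.

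Duration is not counted, because the SAP names no test for it.

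**5. The duplicate tests**

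One binary endpoint was simulated under no effect, with 300 children, arms balanced within strata of site, sex and age group, and 8,000 runs per setting. Event rates (50%, 65%) and covariate strengths were assumed. The chance that the chi-square or the adjusted logistic test is significant was 4.9% to 5.7%, at most 0.7 points above 5%.

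**6. Cost of the alternative, two co-primaries**

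At alpha 0.025 each, power for cognitive falls from 96.0% to 92.9% at SD 6.94, from 89.6% to 83.6% at SD 8, and from 73.1% to 63.1% at SD 10 (SDs assumed). Keeping cognitive as sole primary costs no planned power.

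**The case against.** The strongest reply is that nothing has been taken away. Protocol 6.1 and 6.4.2.1 still name a single primary outcome, and the SAP neither revokes nor replaces it. The SAP is laid out by aim, and protocol Aim 1 (section 2.1) itself covers both service use and development without ranking them. No passage defines trial success as a win on any one endpoint. This stands: the defect is a failure to carry the hierarchy over, and the error rates above describe a misuse that the SAP leaves open, not a rule that it sets.

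Three stronger readings are tempting, and the documents do not support them.
- A reader might infer that a 5% error rate set in the protocol has been lost. No alpha appears in either document, so none was lost; its absence is a gap of its own.
- A reader might infer that testing some hypotheses twice undermines the primary test. The duplicates concern referral completion and initiation only. They never touch the cognitive score, and they add under one point.
- A reader might count five Aim 1 tests and quote a higher error rate. That presumes a test for duration, which the SAP does not name.

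It is also fair to say that protocol 6.4.2.1 already points to a mixed-effects model for the binary outcomes, and that an unadjusted chi-square beside an adjusted model is common practice. The SAP should still say which result governs. Formal multiplicity control of the secondaries would go beyond anything in the protocol and is a preference.

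**Conclusion.** The point holds as a mismatch between protocol and SAP. The SAP ranks no outcome, raises language to the level of the sole primary, gives no analysis for the motor and socioemotional secondaries, and leaves two hypotheses without a test of record. Neither document states alpha, sidedness or a multiplicity rule.

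At an assumed two-sided 5% per test, counting a win on either Bayley score carries a false-positive chance of about 7.0% to 9.75% (correlation 0.9 to 0). Counting any of the four Aim 1 endpoints with a named test carries about 16% to 18.5% (cognitive–language correlation 0.65 with others up to 0.4, through to full independence). These figures apply only if any single win is read as success. The absence of the two promised secondary analyses rests on no assumption. The matter should be corrected, but it does not invalidate the protocol's primary outcome.

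**What to change.** In SAP Aim 1:
1. Name the cognitive composite at 12 months as the sole primary outcome. State alpha and sidedness, for example two-sided 0.05, marked as a new statement because neither document has one.
2. Reconcile the primary model. Protocol 6.4.2.1 gives a linear mixed model with practice clustering; SAP 1c gives logistic regression. Naming the outcome without settling the model would not yield a single primary test.
3. List language, motor, socioemotional, EI referral completion and EI service completion as secondary, with an analysis for each or a stated reason for any omission. Label initiation and duration as additional secondary outcomes.
4. Make the adjusted logistic model the test of record for 1a and for 1b initiation, with the chi-square as descriptive.
5. Label secondary results as supportive and report them with intervals. Holm or fixed-order testing is optional.

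The cost is SAP wording plus the analyses the protocol already promises. Planned power for the cognitive score is unchanged. The downside is that a language-only result could no longer be presented as meeting the primary objective.

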The study research materials will consist of parent- and observer-reported instruments and EI data. Following written informed consent (which is either completed in person or remotely with the electronic REDCap e-consent process), participant caregivers will complete a baseline visit. Measures of demographic characteristics (child age, sex, race/ethnicity, family income, maternal education level, spoken language, and family structure) (Appendix 2), parental health literacy (SAHL) (Appendix 3), and the home learning environment (StimQ) (Appendix 4) will be collected at this visit. Due to the interactive nature of the SAHL measure, in the event that the baseline visit is conducted remotely, the participant will have the option of either completing the measure of parental health literacy (SAHL) remotely by utilizing a video conferencing application or completing the SAHL in-person at a later date. If a visit is conducted using a video conferencing application, we will try to use a HIPAA-compliant application licensed by CHOP (i.e., Skype, Bluejeans or WebEx). Measures of parent engagement and EI referral and service use will be collected at follow-up visits at 3, 6, 9, and 12 months. These visits will be conducted in-person, by telephone, or by email at the preference of the parent. Parents will be asked at study visits to complete the EI Engagement questionnaire, which was adapted from the CECPS and generated during a prior study (IRB 18-014884), and measures of completion of EI referrals (intake, registration, assignment of service coordinator, home visit, and MDE), eligibility for and initiation of EI services (IFSP), EI services use if eligible (number of EI service visits and whether services were completed or terminated), and use of other services (transfer to Preschool EI services, childcare or preschool enrollment). We will corroborate parent-reported visits with EI staff. Participants will also complete the Philadelphia Expanded ACE measure at one time-point throughout the study. This time-point will typically be the 3-month survey, however the measure may be administered during either the 6- 9- or 12-month follow-up survey time-points in the event that the survey is not completed during the 3-month time-point. The ACEs survey assesses for adverse events in that have already occurred in the past (i.e., childhood adverse experiences),

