Measures of engagement will be collected at baseline and at follow-up visits every 3months, while EI referral and service use will be collected at follow-up visits every 3 months. In addition, public policy changes that may impact access to services (e.g. changes in EI funding or eligibility) will be queried of EI staff throughout the study period. The visits will be conducted by research staff blinded to randomization assignment by telephone or email at the discretion of the parent. The Client Engagement in Child Protective Services (CECPS, Appendix 1) is a validated 14-item measure of parent engagement in child welfare services and contains 4 subscales: receptivity, working relationship, buy-in, and mistrust Reliability was good ( $\alpha=0.95$  for the total score and  $\alpha=0.81-0.91$  for subscale scores), and correlation with measures of global engagement and helping relationships and personal support was moderate to strong ( $r=0.36$  to  $0.78$ ). Following discussions with the author of the CECPS (personal communication with [name]), the CECPS will be adapted for an EI population by conducting semi-structured interviews and cognitive testing with a separate group of parents previously referred to EI from one of the urban practices to identify new items and refine the wording on existing items. The adaption of the CECPS measure will be carried out as part of a separate study (IRB 18-014884). We have previously adapted an engagement measure for ADHD using a similar process (See Appendix). Parents will be asked at study visits to complete the adapted CECPS, which we are referring to as the EI Engagement questionnaire, and measures of completion of EI referrals (intake, registration, assignment of service coordinator, home visit, and MDE), eligibility for and initiation of EI services (IFSP), EI services use if eligible (number of EI service visits and duration of EI service visits), and use of other services (transfer to Preschool EI services, childcare or preschool enrollment). We will corroborate parent-reported visits with EI staff.

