Analysis: Test the association between study arm at 3 months and EI referral completion and the association between EI parent engagement at 3 months (mediator) and EI referral completion. If both associations are significant, complete a mediation analysis of the association between study arm and completion of EI referrals, mediated by parent EI engagement.

- b. *Hypothesis 2b:* Completion of EI referrals and participation in EI services (dosage) will mediate the association between program participation (duration), parent engagement, and child developmental status

Analysis of EI referral completion and child development status: Test the association between EI engagement at 3 months and Bayley language & cognitive T scores and the association between MDE completion (mediator) and EI engagement at 3 months. If both associations are significant, complete a mediation analysis of the association between EI engagement at 3 months and Bayley language and cognitive T scores, mediated by EI referral completion.

Analysis of program participation and child development scores: Test the association between program participation and Bayley language & cognitive T scores and the association between referral completion (mediator) and program participation. If both associations are significant,

ODEI Study Statistical Analyses Plan

complete a mediation analysis of the association between program duration and Bayley language and cognitive T scores, mediated by referral completion.

Variable Definitions:

- Program participation: participation in ODEI intervention
- Completion of EI Referrals: Completion of Multidisciplinary Evaluation (MDE)
- Initiating EI services: Date of first early intervention service
- Duration of EI services: The time between the EI service initiation and discharge from early intervention OR 12 months from randomization (if discharge date is unavailable)
- Developmental outcomes: Language and cognitive composite scores from BSID III assessment.
- Parent engagement: total score from 2 subscales on parent engagement (Buy-In/Receptivity to EI and Advocacy/Navigating the EI Process)

Aim 3: To explore whether the home learning environment, parental health literacy, or poverty moderate the effects of the Opening Doors to Early Intervention Program on child developmental status.

a. *Aim 3a:* To explore whether differences in developmental scores between intervention and control groups varies by the richness of home learning environment

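### SAP Aim 2 tests engagement at 3 months against an undated evaluation outcome, so completion may precede the mediator; baseline engagement is not adjusted for

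*SAP*

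**What the plan says.** SAP Aim 2, Hypothesis 2a, names engagement at the 3-month visit as the mediator and tests "the association between EI parent engagement at 3 months (mediator) and EI referral completion". A mediation analysis follows only if this test and the test of study arm against completion are both significant. The outcome is defined as "Completion of EI Referrals: Completion of Multidisciplinary Evaluation (MDE"), with no date attached. The only time frame is in Hypothesis 1a, under which more intervention children "will complete EI referrals than children in the control condition at 12 months".

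The score combines two subscales, "Buy-In/Receptivity to EI and Advocacy/Navigating the EI Process". The Aim 2 analyses name no covariates. Aim 1 does: "logistic regression on the difference in MDE completion by arm, controlling for sex, age, and primary care site".

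Protocol 5.1.2.1 says "Measures of engagement will be collected at baseline and at follow-up visits every 3months", and that "EI referral and service use will be collected at follow-up visits every 3 months". Table 1, section 3.2 and section 4.1.1 also place engagement at baseline. Section 3.1.1 leaves it out of the baseline list and says "Measures of parent engagement and EI referral and service use will be collected at follow-up visits at 3, 6, 9, and 12 months". Protocol 6.4.2.2 defends engagement as a mediator on the ground that it arises after randomisation.

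**The concern.** A mediator has to precede the outcome it is said to explain. Families are recruited at the visit that produces the referral, and navigators then contact them weekly to monthly to move the referral along (protocol 3.1.1 and 7.1.1), so some MDEs may be done within three months. For those children the outcome comes before the engagement score. One of the two subscales concerns navigating the EI process, and a parent who has just been through that process may score higher because of it. Being after randomisation, which is all the protocol argues, does not place engagement before the MDE.

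Randomisation also does not balance engagement against completion. A parent engaged from the start may both score high at 3 months and complete the referral. Baseline engagement is the natural adjustment and no Aim 2 analysis uses it.

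At stake is the mechanistic claim of Aim 2: a positive 2a result could not separate engagement driving completion from completion raising engagement.

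**Working it through.** The documents state no sample size, power or error rate for Aim 2, so there is no figure of the plan's to reproduce. The time order comes from the text; the size is illustrated by simulation.

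**Time order.** Mediator: the 3-month visit. Outcome: any MDE up to 12 months. Recording of referral steps starts at the 3-month visit. Nothing excludes or separates an MDE done in months 0-3.

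**Inputs from protocol 6.5.** 130 control and 170 intervention children with complete follow-up; 50% and 80%, which the protocol gives as EI enrolment rates and which stand in here for MDE completion.

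**Assumed inputs.** Share of completions that are early, f = 0.3, 0.5, 0.8. Rise in engagement after an early MDE, 0.5 SD. Direct programme effect on engagement, a = 0 or 0.3 SD. Engagement has no effect on MDE.

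**Model.** Engagement = N(0,1) + 0.5 × (early MDE) + a × (intervention arm). Path 1 is arm to engagement. Path 2 is engagement to MDE given arm. Both are tested two-sided at 0.05.

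**Expected sizes.** Within an arm, completers exceed non-completers by 0.5f SD: 0.15, 0.25, 0.40. Feedback alone separates the arms by 0.5 × f × (0.80 − 0.50) = 0.15f SD: 0.045, 0.075, 0.12. With SD about 1, the standard error of the arm difference is about √(1/130 + 1/170) = 0.117. Path 1 is therefore rarely significant unless the programme also raises engagement.

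| Early share f | Both paths falsely significant, a = 0 | Same, a = 0.3 SD |
|---|---|---|
| 0.3 | about 1% | about 17% |
| 0.5 | about 3% | about 40% |
| 0.8 | about 17% | about 79% |

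Repeat runs agree within a few points.

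**Size of the spurious effect.** With a = 0, the false indirect effect is about 0.001 to 0.009 of the 0.30 risk difference in these settings. With a = 0.3 SD it reaches about 0.03 in the worst case.

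**Omitting baseline engagement, with no feedback.** This uses a separate logistic simulation (assumed correlation of 0.6 between baseline and 3-month engagement). The engagement-MDE test is falsely significant in 18-21% of trials when baseline engagement raises the log-odds of MDE by 0.25 per SD, and about 63% at 0.5. Adjusting for baseline engagement returns it to 4.2-5.4%.

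**Both problems together** (f = 0.5, feedback 0.5 SD, log-odds 0.25). The same test is falsely significant in 84.3% as written, 62.8% with baseline adjustment alone, and 3.6% with baseline adjustment and restriction to children without an MDE by 3 months.

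**What the restriction leaves.** Expected completers: 130 × 0.5 + 170 × 0.8 = 65 + 136 = 201. At f = 0.8, 161 are early, leaving 300 − 161 = 139 children and 201 − 161 = 40 later MDEs. At f = 0.5 about 199 children and 100 later MDEs remain. At f = 0.8 the restriction removes 0.8 × 0.8 = 64% of intervention and 0.8 × 0.5 = 40% of control children.

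**The case against.** The strongest reply is that the size is assumed throughout. No section gives the share of MDEs done by 3 months or says that an MDE raises engagement, and the questionnaire items are not available. That early MDEs count is itself an inference from an undated definition, a 12-month window and the visit schedule. This stands: the documents show that the analysis cannot exclude reverse order, not that reverse order occurs. The wording of the first 2a test, which attaches the 3-month time point to study arm, is also unclear.

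A reader might take the chance of passing the SAP's two preliminary tests, about 22%, 49% and 89% at the three early shares, as the rate of false mediation claims. It is not. Passing only permits a mediation analysis; the relevant rates are those in the table, and without a direct programme effect on engagement they stay at or below nominal until most completions are early. Against that, the protocol's central hypothesis is that navigation does raise engagement, which makes the higher column the one the trial expects.

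Protocol 6.3 allows further confounders to be added, and 6.4.2.2 builds on models that permit covariates. This helps partly. But 6.3 looks for association with treatment, names no baseline engagement score, and does not address time order.

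Restricting to children without an early MDE has real costs. The set is selected after randomisation, differs by arm and may be small. It belongs in a sensitivity analysis and cannot replace the main one.

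**Conclusion.** The point holds for Hypothesis 2a and for the first 2b analysis, where MDE completion is meant to mediate the effect of 3-month engagement on Bayley scores although the MDE may come first. The second 2b analysis does not use engagement and is unaffected, as are the primary Bayley comparison and Hypothesis 1a. Aim 2 is a secondary objective.

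Followed exactly, the plan can report mediation when completion came first or when early engagement explains both. Under the assumed ranges both paths are falsely significant in about 1-17% of trials with no direct programme effect on engagement, and about 17-79% with a 0.3 SD effect. The true rate is unknown. The spurious indirect effect is small in absolute terms, so the risk is a false significant finding more than a large false estimate.

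A reader might also infer that any 2a mediation result must be spurious, or that exact MDE dates are available to settle the matter. The documents support neither. The SAP defines a date for the first EI service, while the protocol records the MDE as a completion step at quarterly visits.

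**What to change.** In SAP Aim 2:

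1. Adjust the mediator and outcome models for baseline EI Engagement and for sex, age and primary care site.
2. Add a sensitivity analysis of the engagement-MDE association among children with no MDE recorded by the 3-month visit, with later MDE as the outcome. Use status at that visit, or the EI programme record where it carries a date. Apply the same covariates.
3. State that this set is selected after randomisation, differs by arm and may be much smaller, so it gives no randomised arm contrast.
4. Report both estimates with confidence intervals. Describe the all-completions result as an association, and not as evidence that engagement drove completion, unless the post-3-month estimate is consistent with it.
5. Apply the same time-order caution to the first 2b analysis, and clarify the 3-month wording in the first 2a test.

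Reconcile protocol 3.1.1 with Table 1 and sections 3.2, 4.1.1 and 5.1.2.1 on whether engagement is measured at baseline.

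The cost is SAP wording, with no new data if baseline engagement was collected as those sections state. Adjustment is close to free. The restricted analysis loses precision, most of all where early completion is common.
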